10.4.4 Guidelines for reporting adverse events of special interest

10.4.4.1 Reporting of adverse events of special interest (AESI)

For AESIs, the Sponsor must be informed immediately (i.e., within 24 hours), as per SAE notification described in [Section 10.4.3](#) and [Section 17](#), Appendix F even if not fulfilling a seriousness criterion, using the corresponding screens in the e-CRF.

- Allergic events:
 - General allergic drug reactions and/or local injection site reactions deemed to be allergic (or have an allergic component) that require consultation with other physician(s) for further evaluation of hypersensitivity/allergy, as per the Investigator/sub-Investigator's medical judgement or as per [Section 10.6.2](#), should be reported as an AESI with immediate notification.
 - All general allergic events, and all injection site reactions having an allergic component or deemed to be allergic, require completion of the specific e-CRF screen (see [Section 10.6.2](#)), regardless of requirements for immediate reporting.

- Hemolytic anemia (see [Section 17](#), Appendix H):
 - If there is a decrease in hemoglobin and reflexive testing as per [Section 17](#), Appendix H suggesting hemolysis, then report this as AESI with immediate notification. Special e-CRF screen will need to be completed.
- Pregnancy
 - Pregnancy occurring in a female patient or the partner of a male patient included in the clinical trial. Pregnancy will be recorded as an AESI with immediate notification in all cases. It will be qualified as an SAE only if it fulfills the SAE criteria.
 - In the event of pregnancy of a female patient included in the clinical trial, study treatment should be discontinued.
 - The follow-up of the pregnancy will be mandatory until the outcome has been determined.
- Overdose with IMP/NIMP
 - Only the symptomatic overdoses with IMP/NIMP are defined as AESI in the study.
 - An overdose (accidental or intentional) with the IMP/NIMP is an event suspected by the Investigator/sub-Investigator or spontaneously notified by the patient (not based on systematic injection counts).
 - An overdose with the IMP/NIMP is defined as at least twice of the intended dose within the intended therapeutic interval.

10.4.4.2 Device deficiency

A device deficiency is any inadequacy related to the identity, quality, durability, reliability, safety, or performance of the medical device including malfunctions, use errors, and inadequate labeling.

Product complaints:

- A product complaint is defined as any written, electronic, or oral communication that alleges deficiencies related to the identity, durability, reliability, safety, efficacy, or performance of a product after it is released for distribution.
- All product complaints must be reported on a product complaint form when there is a reason to suspect a problem with the device.
- In case of a product complaint associated with the occurrence of an AE, the AE must be documented on an AE page in the CRF.
- In the case of a product complaint associated with the occurrence of a SAE, the SAE must be reported in accordance with the SAE reporting procedure (see [Section 10.4.1.2](#) and [Section 10.4.2](#)).
- All product complaints require reporting within 24 hours

10.4.5 Guidelines for management of specific laboratory abnormalities

Laboratory abnormalities with pre-specified monitoring should be monitored, documented, and managed according to the flowchart shown in [Section 17](#), Appendices G and H.

- Neutropenia
- Thrombocytopenia
- Increase in ALT
- Acute renal insufficiency
- Increase CPK and suspicion of rhabdomyolysis
- Decrease in hemoglobin (defined as ≥ 1.5 g/dL)

10.4.6 Summary of adverse event reporting instructions

[Section 17](#), Appendix F shows the summary of the reporting instructions of adverse events.

10.5 OBLIGATIONS OF THE SPONSOR

During the course of the study, the Sponsor will report in an expedited manner;

- All SAEs that are both unexpected and at least reasonably related to the IMP (Suspected Unexpected Serious Adverse Reaction, SUSAR), to the Health Authorities, independent ethics committees (IECs) / institutional review board (IRB) as appropriate and to the Investigators.
- All SAEs that are expected and at least reasonably related to the IMP to the Health Authorities, according to local regulations.

Any AE not listed as an expected event in the Package Insert will be considered unexpected.

The Sponsor will report all safety observations made during the conduct of the study in the CSR.

10.6 SAFETY INSTRUCTIONS

10.6.1 Local tolerability (local injection site reactions)

In case the Investigator/sub-Investigator or the patient recognize any sign of local intolerance, then this should be treated and followed up as per the Investigator/sub-Investigator's medical judgment. See [Section 17](#), Appendix I for further information.

AEs that are obviously not of allergic origin (e.g., local injection site reactions) should only be recorded on the Local Injection Site Reaction Complementary Form. However, injection site reactions which progress/expand/worsen/etc., should be evaluated and General Allergic Reaction Complementary Form should be completed.

10.6.2 Allergic adverse events

Specific e-CRF screen are to be filled in to access allergic reactions or allergic-like reactions that may occur during the study conducted with Praluent®. Sometimes transient injection site reactions, irritant in nature, may occur, requiring no intervention and being of dubious significance. These reactions would not be considered to be allergic reactions. Adverse events that may constitute an allergic reaction (e.g., generalized itch, nasal itch, swelling at injection site, flushing, hives, swelling at lips, eyes, face, tongue, hands, feet, lump in throat, difficulty in swallowing, hoarseness, change in pitch of voice, incapacity to speak, wheezing, chest tightness, stridor, etc.) should be considered to be reported on the General Allergic Reaction and/or Local Injection Site Reaction Complementary Form.

Adverse events that are obviously not of allergic origin (e.g., local injection site reactions related to mechanics of injection) should only be recorded on the Local Injection Site Reaction Complementary Form. However, injection site reactions that progress/expand/worsen/etc. should

be evaluated as recommended in [Section 10.6.2](#) and the General Allergic Reaction Complementary Form should be completed.

The IMP should be immediately interrupted (temporarily discontinued) if there is a suspicion of an allergic event related to IMP. See [Section 10.3.1](#) for further information on treatment interruption and [Section 10.3.3](#) for criteria for permanent treatment discontinuation.

10.6.2.1 Allergic adverse events with cutaneous involvement

AEs with cutaneous involvement which are obviously of allergic origin or injection site reactions which progress/expand/worsen/etc. should be evaluated by dermatologist as soon as possible, and preferably within one week of the study site first becoming aware of the event.

The Investigator/sub-Investigator should evaluate the patient for possible etiologies (new medications, etc.) and extra-cutaneous symptoms and signs. If possible, the Investigator/sub-Investigator will take pictures of skin lesions in order to provide the patient with the abnormal skin images for the dermatologist's visit. If the photographs of skin lesions are obtained, then photocopies should be kept as source documents which may be collected by the Sponsor later. The Investigator/sub-Investigator will provide summary of the patient's case, reason for consultation, and information being requested to the consulting dermatologist.

A full consultation report should be sent by the dermatologist to the Investigator. The full report should contain, at a minimum, the following instruction; 1) A detailed description of the rash (such as the morphology [lesion type], shape of individual lesions, arrangement of multiple lesions [e.g., scattered, grouped, linear, etc.], distribution, color, consistency, presence of pruritus or pain, and other clinical signs); 2) Findings of skin biopsy (including histopathology and immunofluorescence) if it was deemed necessary as per the dermatologist's or Investigator/sub-Investigator's medical judgment; and 3) The results of this investigation with, if applicable, a specific diagnosis of the AE. The Investigator/sub-Investigator will fax the full report and the corrected AE form if necessary, to the Sponsor within 24 hours.

10.6.2.2 Acute allergic reactions of IMP injection

See also [Section 10.4](#).

Acute allergic reactions of IMP (which is considered under the category of general allergic reactions) is defined as any AE that occurs during or shortly after injection of Praluent® (characterized by but not limited to hypotension, bronchoconstriction, urticaria, edema, angioedema, nausea, vomiting). Emergency equipment and medication for the treatment of these potential adverse effects (e.g., antihistamines, bronchodilators, saline, corticosteroids, acetaminophen, and epinephrine) must be available for immediate use of the injections at the study site.

Patients will be observed at the investigational site for at least 30 minutes following the injection that takes place at the randomization visit. Patients should be treated symptomatically if any AE is observed. Patients are to remain at the study site until any acute injection reaction is assessed as stable, per the Investigator/sub-Investigator's discretion.

General Allergic Reaction and/or Local Injection Site Reaction Complementary Form will have to be completed.

10.6.3 Cardiovascular events and all deaths

The following suspected or confirmed CV events that occur from randomization until end of the study visit should be reported in a corresponding specific e-CRF. The Investigator will submit the adjudication materials to the CEC through the Sponsor as needed:

- MI.
- Congestive heart failure requiring hospitalization.
- Cerebrovascular events (e.g., stroke, transient ischemic attack, intracranial hemorrhage, ischemia or bleeding of spine or retina).
- Unstable angina requiring an emergency room visit or requiring / prolonging hospitalization.
- All coronary revascularization procedures (e.g., PCI, coronary artery bypass graft).
- All death (including CHD death).

All suspected or confirmed CV events should be reported as SAEs. For coronary revascularization procedures, medical or surgical procedure should not be reported as an adverse event, but rather, the reason for the procedure should be reported as the adverse event (e.g., unstable angina leading to PCI should be reported as “unstable angina” instead of “PCI”).

10.6.4 Laboratory alert related to calculated LDL-C <25 mg/dL (0.65 mmol/L)

The process includes specific assessment and monitoring in all patients, who has the calculated LDL-C values <25 mg/dL (0.65 mmol/L) any time after the randomization:

- The patient will continue study treatment (both alirocumab and SoC arms).
- The Investigator closely monitors the patient and collects any AE including AEs potentially associated with low LDL-C.
- The Investigator/sub-Investigator decides whether patient should be immediately request to have an unscheduled on-site visit, or patient assessment could be done at the next scheduled on-site visit.
- At the on-site visit, plan for the following, based on the Investigator/sub-Investigator’s medical judgment:
 - Assess the need for conducting clinical investigations, arranging specialist consultation(s) as needed, and any relevant additional work-up.
- Assess the need for temporary or permanent discontinuation of study treatment, or continuation of the study treatment. Regardless of the action taken regarding study treatment, the patient should continue the study as per [Section 10.3](#).

11 STATISTICAL CONSIDERATIONS

11.1 DETERMINATION OF SAMPLE SIZE

The study is expected to enroll approximately 200 patients. The sample size calculations are based on the primary efficacy variable of percent change in normalized TAV from baseline to Week 36.

Based on the results of ZEUS (1) and PRECISE-IVUS (2) studies, it is assumed that difference in percent change in normalized TAV from baseline between alirocumab arm and SoC arm is 8%, and the common standard deviation of percent change in normalized TAV is 15%.

Under the assumption, a sample size of 150 patients (75 in the alirocumab arm and 75 in the SoC arm) will have 90% power to detect the treatment difference with two-sided significance level of 5%. Assuming that proportion of non-evaluable primary endpoint is 25%, it is considered that 200 patients (100 in the alirocumab arm, 100 in the SoC arm) will be needed.

As the ANCOVA model will be used for primary analysis, the power should be somewhat higher due to reduced estimate variability versus the two-sample t-test.

Calculations were made using SAS 9.4

11.2 DISPOSITION OF PATIENTS

Patients who signed the informed consent are defined as the patients who signed the informed consent.

Randomized patients consist of all patients who have been allocated to a randomized treatment and recorded in the registration center database, regardless of whether a study drug was used or not.

Patients treated without being randomized will not be considered as randomized and will not be included in any analysis population.

For any patient randomized more than once, only the data associated with the first randomization will be used in any analysis population. The safety experience associated with any later randomization will be assessed separately.

The safety experience of patients treated and not randomized will be reported separately.

11.3 ANALYSIS POPULATIONS

The randomized population includes all randomized patients defined in [Section 11.2](#).

11.3.1 Efficacy populations

The primary efficacy analysis population will be the modified intent-to-treat (mITT) population, as defined below.

11.3.1.1 Modified intent-to-treat population

The modified intent-to-treat population is the randomized population which takes at least one dose or part of dose of study drug and has an available value of normalized TAV before randomization, and after 24 weeks of treatment. Patients will be analyzed in the treatment arm to which they are randomized.

11.3.2 Safety population

The safety population is defined as the randomized population which actually received at least 1 dose or part of a dose of the study drug, and analyzed according to the treatment actually received.

In addition:

- Non-randomized but treated patients will not be part of the safety population, but their safety data will be presented separately.
- Randomized patients for whom it is unclear whether they took the study drug will be included in the safety population as randomized.
- The treatment arm allocation for “as-treated analysis” will be defined as follows:
 - Alirocumab arm if proportion of IMP injection is $\geq 50\%$.
 - SoC arm if proportion of IMP injection is $<50\%$.
- Proportion of IMP injection (%) is defined as $100 \times (\text{Number of IMP injection}) / [(\text{Date of end of treatment} - \text{Date of randomization})/14 + 1]$

11.3.3 Quality-of-life (QOL) population

The analyses of QOL will be performed on all randomized and treated patients (safety population) with a baseline and at least 1 matching post-baseline evaluation for any of the 5 dimensions.

11.4 STATISTICAL METHODS

Statistical methods are briefly described here and will be detailed in the statistical analysis plan (SAP) of the study.

11.4.1 Extent of study treatment exposure and compliance

The extent of study treatment exposure and compliance will be assessed and summarized within the safety population. The extent of IMP exposure and compliance will be summarized for alirocumab arm (actual treatment received). Regarding to NIMP, it will be detailed in the SAP.

11.4.1.1 Extent of investigational medicinal product exposure

The total exposure will be assessed by:

- Duration of IMP exposure in weeks regardless of intermittent treatment is defined as: (last dose of IMP injection date – first dose of IMP injection date + 14 days)/7.
- Number (%) of patients with an up-titration from Praluent® 75 mg Q2W to Praluent® 150 mg Q2W.

11.4.1.2 Compliance of investigational medicinal product exposure

Compliance will be assessed using the injection frequency defined for each patient as the average number of days between 2 injections, that is: (last injection date - first injection date) / (number of injections - 1) and will be summarized descriptively (N, Mean, SD, Median, Min and Max).

11.4.2 Analyses of efficacy endpoints

11.4.2.1 Analysis of primary efficacy endpoint

The primary efficacy endpoint, percent change in normalized TAV from baseline to Week 36 defined in [Section 9.1.1](#) will be analyzed in the mITT population using an analysis of covariance (ANCOVA) model with treatment arm (SoC arm, alirocumab arm) and randomization strata (statin at ACS onset [Yes / No]), as fixed effects, and the baseline normalized TAV as covariate.

Throughout the ANCOVA model run using SAS Mixed procedure, alirocumab arm will be compared to SoC arm at the two-sided 0.05 level for superiority and providing baseline adjusted least squares means (LS means) estimates at Week 36 for each treatment arm with their corresponding standard errors (SEs) and the 95% confidence interval (CI) of the difference between the arms.

Let μ_0 and μ_1 be the population means of the percent change in normalized TAV from baseline to Week 36 under SoC arm and alirocumab arm, respectively. The null hypothesis that will be tested is " $H_0 : \mu_0 = \mu_1$ " versus " $H_1 : \mu_0 \neq \mu_1$ ".

Robustness of this method will be also assessed via sensitivity analyses detailed in the SAP, including for handling of missing data.

11.4.2.2 Analyses of secondary efficacy endpoints

Method for controlling the overall type-I error rate when testing the key secondary efficacy endpoint is described in [Section 11.4.2.3](#).

For the key secondary efficacy endpoint (defined in [Section 9.1.2.1](#)) and the other secondary efficacy endpoints (described in [Section 9.1.2.2](#)), descriptive summaries and analyses will be performed in the mITT population.

For descriptive summaries, percentage change (except ratio) and absolute change from baseline in calculated LDL-C, TC, HDL-C, TGs, non-HDL-C, Apo B, Apo A-1, Apo B/Apo A-1 ratio, and Lp(a) will be provided at each time point for each treatment arm. For lipids, all measurements, scheduled or unscheduled will be assigned to analysis windows defined in the SAP in order to provide an assessment for time points. Laboratory assessments other than the ones provided by the central laboratory will be excluded. For TGs, measurements on non-fasting patients will be excluded. The time profile of each parameter will be plotted by treatment arm with the corresponding SEs.

Continuous endpoints related to IVUS anticipated having a normal distribution

Continuous secondary endpoints related to IVUS anticipated having a normal distribution will be analyzed using the same ANCOVA model as for the primary endpoint with the continuous fixed covariates of corresponding baseline value.

Continuous endpoints of lipids anticipated having a normal distribution and collected at Week 0, Week 4, Week 12, Week 24 and Week 36

Continuous secondary endpoints of lipids defined in [Section 9.1.2](#) are anticipated having a normal distribution and collected at Week 0, Week 4 Week 12, Week 24, and Week 36 (i.e., calculated LDL-C, TC, HDL-C, non-HDL-C) will be analyzed in the in the mITT population using a mixed-effect model with repeated measures (MMRM) approach. All post-baseline data available within Week 4, Week 12, Week 24, and Week 36 analysis windows will be used and missing data will be accounted for by the MMRM model. The model will include the fixed categorical effects of treatment arm (SoC arm, alirocumab arm), time point (Week 4, Week 12, Week 24, and Week 36), randomization strata (statin at ACS onset [Yes / No]), treatment-by-time point interaction, randomization strata-by-time point interaction, as well as, the continuous fixed covariates of corresponding baseline value and baseline value-by-time point interaction.

Continuous endpoints of lipids anticipated having a normal distribution and collected at Week 0 and Week 36

Continuous secondary endpoints of lipids defined in [Section 9.1.2](#) are anticipated having a normal distribution and collected at Week 0 and Week 36 (i.e., Apo B, Apo A-1, Apo B/Apo A-1 ratio) will be analyzed using the same ANCOVA model as for the primary endpoint with the continuous fixed covariates of corresponding baseline value.

Continuous endpoints of lipids anticipated having a non-normal distribution

Continuous secondary efficacy endpoints of lipids defined in [Section 9.1.2](#) are anticipated having a non-normal distribution (i.e., TGs and Lp(a)), will be analyzed in the mITT population using a robust regression model ([37](#)) (i.e., ROBUSTREG SAS procedure with M-estimation option) with treatment arm, and randomization strata (statin at ACS onset [Yes / No]) as main effect and corresponding baseline value(s) as covariate. Missing values will be addressed using a multiple imputation approach, which will be described in the SAP. The variables in the multiple imputation model will at least include the same variables as used in the robust regression model. The treatment arm combined means will be provided with respective SE estimates. The combined mean difference between the treatment arms will be provided with the SE, 95% confidence interval and p-value.

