9.1.2.2 Other secondary efficacy endpoints

The other secondary efficacy endpoints are:

- Absolute change in normalized TAV from baseline to Week 36.
- Absolute and percent changes in external elastic membrane (EEM) volume from baseline to Week 36.
- Absolute and percent changes in lumen volume from baseline to Week 36.
- Absolute and percent changes in calculated LDL-C from baseline to Week 12, and Week 36.
- Absolute and percent changes in Apo B from baseline to Week 36.
- Absolute and percent changes in non-HDL-C from baseline to Week 36.
- Absolute and percent changes in TC from baseline to Week 36.
- Absolute and percent changes in Lp(a) from baseline to Week 36.
- Absolute and percent changes in HDL-C from baseline to Week 36.
- Absolute and percent changes in fasting TGs from baseline to Week 36.

- Absolute and percent change in Apo A-1 from baseline to Week 36.

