11.4.5 Analyses of quality of life/health economics variables

The analysis of QOL data will be performed on the QOL population. Baseline is defined as the visit 1 (week 0) evaluation.

Data on the 5 items

The responses of each EQ-5D items will be presented by visit for each treatment arm using tables. The tables will contain information on the frequency and proportion of the population reporting level 1 (no problems), level 2 (some problems) and level 3 (extreme problems) per item, by treatment arm.

Scoring the EQ-5D health states

The 5 dimensional 3-level system will be converted into a single index utility score: values for the 243 theoretically possible health states defined by the EuroQol classification are calculated using a regression model (36). The single index utility score will be described by visit and treatment arm.

Absolute change from Baseline to the following time points

The absolute change of health-related QOL (single index utility score) from baseline to following time points will be described in the QOL population for each treatment arm using the same MMRM model as for the continuous secondary efficacy endpoints of lipids anticipated to have a normal distribution and collected at Week 0, Week 4, Week12, Week 24 and Week 36 with corresponding baseline value as covariate.

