### **2.3.1 Efficacy populations**

#### **2.3.1.1 *Modified intent-to-treat population***

The primary efficacy analysis population will be the modified intent-to-treat (mITT) population, defined as the randomized population who took at least one dose or part of dose of study drug, and has 2 analyzable normalized TAV, as defined below.

- One assessed before randomization
- Another one assessed after 24 weeks of treatment.

Patients in the mITT population will be analyzed according to the treatment group allocated by randomization.

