### **2.3.3 Quality-of-life population**

The analyses of QOL will be performed on all randomized and treated patients (safety population) with a baseline and at least 1 matching post-baseline evaluation for any of the 5 dimensions. Patients will be analyzed according to the treatment actually received.

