##### ***Continuous endpoints anticipated to have a normal distribution with multiple post-baseline values collected***

Continuous secondary endpoints anticipated to have a normal distribution with multiple post-baseline values collected (i.e., calculated LDL-C, TC, HDL-C, non-HDL-C) will be analyzed in the mITT population using a mixed-effect model with repeated measures (MMRM) approach. All post-baseline data available within Week 4, Week 12, Week 24, and Week 36 analysis windows

will be used and missing data are accounted for by the MMRM model. The model will include the fixed categorical effects of treatment group (SoC group, Alirocumab group), time point (Week 4, Week 12, Week 24, and Week 36), randomization strata (statin at ACS onset [Yes / No]), treatment-by-time point interaction, randomization strata-by-time point interaction, as well as, the continuous fixed covariates of corresponding baseline value and baseline value-by-time point interaction.

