### ***EQ-5D utility score***

The raw value and the absolute change from baseline of the utility score will be summarized using mean, median, Q1, Q3, SD, minimum, and maximum for each post-baseline visit. Cumulative distribution functions for the absolute change in utility score from baseline will be displayed by treatment groups, at Week 4, Week 12, Week 24, and Week 36.

The absolute change from baseline in utility score to Week 4, Week 12, Week 24, and Week 36 will be analyzed using a MMRM model with fixed categorical effects of treatment group, randomization strata as per the registration center, treatment-by-time point interaction, strata-by-time point interaction, as well as, the continuous fixed covariates of baseline value and baseline value-by-time point interaction.

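### Every lipid efficacy analysis, including Week 12 LDL-C, is limited to patients with an analyzable IVUS on day 169 or later; an analysis by randomized arm regardless of IVUS should be added

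*Protocol*

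**What the plan says.** Protocol 11.4.2.2 and SAP 2.4.4.2 use the same sentence for the key and all other secondary efficacy endpoints: "descriptive summaries and analyses will be performed in the mITT population". The restriction is repeated for the MMRM (LDL-C, TC, HDL-C, non-HDL-C), for the robust regression of Lp(a) and for the multiple imputation of TGs. The ANCOVA endpoints (Apo B, Apo A-1 and ratios) and the SAP's LDL-C responder endpoints fall under the general sentence.

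Membership of mITT needs at least part of one dose, and SAP 2.3.1.1 adds that the patient "has 2 analyzable normalized TAV, as defined below": one before randomization and one after 24 weeks of treatment. SAP Table 3 opens the IVUS window on day 169.

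Protocol 9.1.2.2 lists as endpoints "Absolute and percent changes in calculated LDL-C from baseline to Week 12, and Week 36". SAP Table 4 sets the Week 12 lipid window at days 78 to 98.

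Of the repeated lipid measurements, the SAP says that all post-baseline data in the analysis windows "will be used and missing data are accounted for by the MMRM model".

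EQ-5D, collected at the same five visits, has no imaging condition. Its population needs only treated patients "with a baseline and at least 1 matching post-baseline evaluation for any of the 5 dimensions" (Protocol 11.3.3), and Protocol 11.4.5 analyses the index score "using the same MMRM model as for the continuous secondary efficacy endpoints of lipids".

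**The concern.** A blood value at Week 12 does not depend on a later catheter procedure, yet a patient's Week 12 LDL-C counts only if an analyzable image is obtained months afterwards. This is selection on a post-randomization outcome. The sentence about the MMRM gives the impression that missing data are handled. They are handled only among patients who already have the later image; those who left early contribute no Week 4 or Week 12 values and are not imputed.

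The selection could differ by arm. Under Protocol 10.3.3, the low-adherence discontinuation criterion is read over 12 weeks of injections in the alirocumab arm. In the SoC arm it is read over 6 months of background medication, with investigator discretion at 3 months. Under Protocol 10.3.4, a patient who leaves before Week 24 is offered an early end-of-treatment visit, but an image taken before day 169 would not qualify. Adherence can plausibly influence both LDL-C and mITT membership.

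At stake are the randomized comparison of Week 12 LDL-C and the use of lipid samples that the protocol already schedules.

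**Working it through.** **1. Reproduce the plan's sample size (Protocol 11.1, SAP 1.3).** Difference 8, SD 15, two-sided 5%. With 75 per arm, the exact t-test power is 0.9006, matching the stated 90%. Inflating for 25% non-evaluable: 150 / 0.75 = 200. Expected outside mITT: 200 × 0.25 = 50.

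**2. Gap between the endpoint and the condition on it (SAP Tables 3 and 4).** Earliest qualifying image: 24 × 7 + 1 = day 169. End of the Week 12 window: day 98. Gap: 169 − 98 = 71 days at least. From the Week 12 target day it is 169 − 85 = 84 days.

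**3. Does any other planned lipid efficacy analysis include the excluded patients?**
- Randomized-population imputation (SAP 2.4.4.1 and its counterpart in 2.4.4.2): normalized TAV and PAV only.
- Per-protocol analyses: a subset of mITT, covering IVUS parameters only.
- MMRM, robust regression, TG imputation: mITT.

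So none does. Outside the efficacy analyses, some lipid data from these patients are used: the counts of two consecutive LDL-C values below 25 or 15 mg/dL, the alirocumab titration summary (both in the safety population), the baseline tables, and baseline lipids in the imputation model for the primary endpoint.

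**4. Precision at Week 12.** Assume that all 150 mITT patients have the value, variances are equal and arms are balanced, and that m of the 50 others also have one. SE ratio, mITT to wider set = √((150 + m)/150).

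| Share of the 50 with a value | m | Ratio | mITT SE larger by |
|---|---|---|---|
| 25% | 12.5 | √(162.5/150) = 1.041 | 4.1% |
| 50% | 25 | √(175/150) = 1.080 | 8.0% |
| 100% | 50 | √(200/150) = 1.155 | 15.5% |

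**5. Precision at Week 36 if the added patients have only an early value.** Assume data missing completely at random and a correlation r between the early and Week 36 values of 0.5 to 0.8 (not in the documents). SE factor = √(1 − r² × m/(150 + m)).

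| m | r = 0.5 | r = 0.8 | SE lower by |
|---|---|---|---|
| 12.5 | 0.990 | 0.975 | 1.0% to 2.5% |
| 25 | 0.982 | 0.953 | 1.8% to 4.7% |
| 50 | 0.968 | 0.917 | 3.2% to 8.3% |

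**6. Apo B, Apo A-1 and Lp(a).** The flow chart schedules one post-baseline sample, at Week 36. A patient who leaves before Week 24 and is sampled within the preferred 7 days gives it by about day 168 + 7 = 175, which is 239 − 175 = 64 days before the Week 36 lipid window opens. These endpoints gain only where a true Week 36 sample exists.

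**7. How selection would act on an arm mean.** Shift in the retained mean = share excluded × (retained mean − excluded mean). At 25% excluded, assumed gaps of 10, 20, 30 and 40 percentage points give 2.5, 5.0, 7.5 and 10.0. If exclusion is unrelated to response, the shift is zero. Only a difference in shift between arms biases the treatment comparison, and the documents give no information on the gap in either arm.

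**The case against.** The strongest reply is that this is a plaque trial, and that reporting lipids in the patients who supply the plaque result lets LDL-C and TAV change be read together. That stands, and is a reason to keep the mITT lipid analysis. It is not a reason for Week 12 LDL-C to have no other analysis.

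Further points on that side also stand:
- The lipid objective (Protocol 5.2) concerns 9 months, not Week 12. Week 36 lipids and the evaluation IVUS belong to the same visit, so patients without the image will often lack Week 36 lipids too. A reader might infer that the 9-month objective is seriously compromised; step 5 does not support that.
- The 25% is non-evaluability from any cause. It also covers patients with no dose or no usable baseline TAV, so it would be wrong to read all 50 as lacking only the later image.
- The SE figures measure lost precision, not bias. A reader might infer that the planned result is biased, perhaps in favour of alirocumab. The documents show a possible route, not that it operates or in which direction.
- A 4% to 15.5% wider SE matters little if the effect is near the −61.5% at Week 12 reported for the Japanese phase 3 study (Protocol section 4), although the comparator there was placebo.
- EQ-5D is a precedent, not a contradiction. In the SAP its patients are analysed as treated ("Patients will be analyzed according to the treatment actually received"), and its index score "will be analyzed using a MMRM model with fixed categorical effects of treatment group", in a list that omits a time-point main effect. The safety-based set should not simply be borrowed for lipids.

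**Conclusion.** The conditioning is certain: it follows from the mITT definition and the two window tables, and no planned lipid efficacy analysis escapes it. The claim that the MMRM accounts for missing data is true only within mITT. Whether bias results, how large and in which direction, cannot be settled from the documents.

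The practical case rests on Week 12 LDL-C. There the restriction makes the randomized comparison depend on a later image and gives an SE about 4% to 15.5% larger than in the wider set, if 25% to 100% of the roughly 50 non-evaluable patients have a value. For the 9-month objective the precision gain is about 1% to 8% under the assumed correlations, and for Apo B, Apo A-1 and Lp(a) it may be nil.

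Primary and key secondary results are untouched, and Protocol 11.4.2.3 and SAP 2.4.4.3 make the other secondary p-values exploratory. The change should be made because it is cheap and removes avoidable selection; the trial's main conclusions do not depend on it.

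**What to change.** Before database lock, add to SAP 2.4.4.2 a prespecified analysis of the repeatedly measured lipids (LDL-C, TC, HDL-C, non-HDL-C, fasting TGs), above all Week 12 LDL-C:
- Population: randomized patients with a baseline and at least one post-baseline central-laboratory value, regardless of IVUS. A patient can then enter from day 15, when the Week 4 window opens, instead of day 169.
- Analysis by randomized arm, with the models already planned.
- The Week 12 LDL-C conclusion rests on this analysis.
- The mITT lipid analysis stays, so that lipid and plaque change can be read in the same patients.

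Costs: one population flag and an extra table set, using samples already scheduled. Lipid and IVUS results will have different denominators, which the tables should state. The set still requires one post-baseline value, and laboratory visits after discontinuation are requested, not assured (Protocol 10.3.4).

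At Week 36, patients who left early would be handled under a missing-at-random assumption, in the MMRM or through imputation. For those who stopped treatment this may project on-treatment values forward. The SAP should say so and read the Week 36 result accordingly.

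A supplementary SAP analysis leaves the protocol unchanged. If Protocol 11.4.2.2 is amended as well, section 15 requires IRB/IEC approval.
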